3. Able to speak, read and write fluently in English, assessed by the study coordinator at Carrier Clinic
4. Screened Negative for alcohol abuse and/or dependence
5. Able to provide informed consent, assessed by the study coordinator at Carrier Clinic
6. Referred for ECT
7. Not currently taking hypnotics or be prescribed hypnotics during the Nexalin trial.
8. Not pregnant or intending to become pregnant during the study
9. Committed to completion of the study.

TOTAL SUBJECTS ENROLLED

150

VULNERABLE POPULATIONS

No vulnerable populations (as defined by socio-economic status, geography, gender, age, disability status, and other populations identified to be at-risk for health disparities) will be recruited.

RECRUITMENT & RANDOMIZATION

As noted above, patients will be directly recruited from, and receive treatment at, the Carrier Clinic. Currently, the Carrier Clinic treats approximately 1,000 unique patients who receive ECT annually, resulting in 5,200 procedures performed per year. Randomization will occur in blocks, such that for every 20 subjects enrolled, 10 will receive Nexalin and 10 will receive Sham treatment.

COMPENSATION

No financial compensation will be provided to participants for participation in the trial.

PRIMARY OUTCOMES

Percent responders and non-responders to TES treatment or Sham TES treatment (who accepted or refused ECT) as assessed with the PHQ-9 (50% reduction or a score below 10).

SECONDARY OUTCOMES

Assess whether Nexalin TES produces significantly greater gains than Nexalin Sham for

1. Depression severity (as assessed with the PHQ-9, and the QIDS)
2. Anxiety severity (as assessed with the GAD-7 and the POMS)
3. Insomnia severity (as assessed with the ISI)

Finally, we will (post hoc) assess which baseline subject characteristics differentiate between responders and non-responders.

PROCEDURES

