All patients referred for ECT and otherwise eligible for the study will be approached by the Carrier Clinic study coordinator (or his designate) and asked whether they wish to participate in the research study. All subjects will be non-responders to traditional medical approaches (patients diagnosed with MDD who have failed antidepressant therapy with one or more medications). Those that express interest will review the study protocol with the study coordinator. The study coordinator will ascertain eligibility, address any concerns, and obtain written informed consent. Following the obtention of informed consent, the subject will be scheduled (or undergo at the time) a baseline assessment. The subjects that volunteer, are eligible, and are consented for the study will be queried as to whether or not they are willing to receive ECT. This decision will be used to type each subject that consents to be in the protocol (Accept or Refuse ECT). Following randomization to one of two conditions (TES or Sham), treatment will occur twice daily (40 minutes per session, separated by 5 hours' time between the AM and PM sessions) over 3-10 days. Subjects that do not exhibit 20% attenuation of symptoms (as assessed by an AM and PM version PHQ-9) on or before 6 treatments will be designated treatment non-responders and discontinue their participation in the study while remaining as inpatients at the Carrier Clinic. Note: During the Nexalin trial, all subjects will receive standard inpatient care where the only difference in the treatment regimens are that they are receiving TES or Sham TES in place of ECT. See "Protection Against Risks" section for stopping rules during treatment for subjects who do not show sufficient treatment response.

Session Protocol. The protocol for receiving treatment will be as follows:

1. Inpatients that have enrolled in the study will receive TES or Sham TES once in the AM and once in the PM.
2. The procedure will be conducted in a semi-private room while the subject reclines in a lounge chair.
3. The two TES session will each be 40 minutes in duration, separated by 5 hours' time.
4. The TES provider will oversee the administration of the patient on-line questionnaires.
5. The TES trained provider will complete the Carrier Clinic staffforms.
6. When the TES session is complete, the subject will resume his/her regular clinic activities.

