Treatment. As noted above, Nexalin TES or Sham TES will be administered twice per day (9am noon and then again 2pm-5pm), Monday through Friday, over the course of 3-10 days. Each patient will receive a minimum of 6 treatments and may receive up to 20 treatments depending on whether an adequate treatment response is observed during the first 6 session (this is based on the assessments overseen by the Penn staff based on the AM/PM PHQ-9 evaluations). All procedures will be performed at the Carrier Clinic facility by licensed

personnel with experience providing care to medication non-responders and will be specially trained on using the Nexalin equipment. Nexalin TES involves placing three conductive pads on the head (one on the forehead and one behind each ear). The patient then sits as the device administers the current through the pads. The waveform generated by the Nexalin device is a high frequency square wave (100 kHz), which has its amplitude modulated at a frequency of 77.5 Hz. Amplitude of the waveform (square wave pulse) is controlled to range from 0 to 4 mA peak current (off is 0 mA and on is 4mA). Each treatment session will last for 40 minutes. The treatment is not expected to be painful, but some individuals may experience discomfort (i.e. tingling and burning). In most cases, patients cannot feel when the pads are activated. The Sham treatment will be identical with the exception that there will be no current through the electrodes. Since the Nexalin treatment is undetectable, this will exactly mimic active treatment.

Assessments. Assessments will be made at baseline (pre-treatment), twice daily, once daily, and once every 3 days (6 sessions). All assessments will be administered on-line via two web-sites dedicated to the study (1 website for the subjects and one website for the clinical staff). The subject web-site will contain 10 questionnaires. The staff website will contain 5 forms.. See figure below for a specification of the specific instruments and schedule of administration. The site itself will be built using Research Electronic Data Capture (REDCap) software. Note: All data acquired via this method (raw and summary data) will not be available to the Carrier Clinic collaborators during the study.

	#	Instrument	Time Required	Baseline	Each Session	Q 3 days	Pre-Post	PRN
Patient	1	Demographics	5 min	●				
	2	AFQ & CAGE	2 min	●				
	3	Patient Expectancy	1 min	●				
	4	QIDS	5 min	●		●		
	5	ISI	2 min	●			●	
	6	SAFETEE	5-10 min	●		●		

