5. ISI (Completed at baseline and at the end of treatment): The Insomnia Severity Index is a brief insomnia screening tool that is the gold standard for quantifying severity of clinical insomnia symptoms. This will be administered at the beginning and end of treatment (e.g., 1st and 10th session).
6. SAFTEE (completed once every 3 days): The Systematic Assessment of Treatment-Emergent Effects was developed by the NIH to comprehensively catalog any physical symptoms experienced during psychiatric clinical trials along 16 subscales. This measure will be used to systematically measure symptoms and symptom categories.
7. PHQ-9 (completed in the AM and PM session): The Patient Health Questionnaire 9 is a brief, well-validated screening tool for depression. It has shown good reliability and validity for likely depression diagnosis and provides a means of assessing depression severity. The instrument in the present study has been modified so that it may be 1) administered twice daily and 2) used to track nightly sleep via 4 sleep related items
8. GAD7 (completed at baseline and once every 3 days): The Generalized Anxiety Disorder 7 questionnaire is a brief global screening measure of anxiety. It is well validated and is a standard screening tool for anxiety. This scale will allow for separate characterization of anxiety symptoms in addition to depression.
9. POMS (completed at baseline and once every 3 days): This is a 37-item adjective checklist where each item is rated on a 0-4 unipolar scale that ranges from not-at-all to extremely. The scored instrument provides values for six constructs including: tension-anxiety; depression-dejection; anger-hostility; fatigue-inertia; vigor-activity; and confusion-bewilderment. The outcome variables are measured in terms of the 6 factors and a total score, which are arrayed as T-Scores (standardized means of 50 +/-10).
10. “Faces” Mood Rating Scale (completed daily pre-post to each TES session): This is a single item 7 point bipolar rating scale for mood (from very happy to very sad). The measure is arrayed from -3 to +3.

Clinician Measures. All the clinician instruments to be used in the study are listed below along with their administration schedule and brief explanation regarding what the instrument measures

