1. Patient Enrollment Form / Candidate Screener / Enrollment Form (completed once per week per patient): This requires the staff member to profile the patient who has been approached to participate in the study and to document if they meet eligibility and have been consented.
2. Procedure Tracking form / Patient Tracking (once per session): This requires the clinician to record: the patient initials; the patient PNC ID; the date of the session; the session #; the time session was conducted; the room the session was conducted in; the identifying sticker attached to the device; the device number; whether each instrument was administered; any comments they may have about the session; whether the

patient was diagnosed with any new disorders (and if yes, please list); and whether the patient's meds have been changed (and if yes, please list).

3. Adverse Event Form (*completed as needed*): This requires the clinician to record: the patient initials; the patient PNC ID; the date of the session; description of event; information about the event onset; start date and start time of event; information about the event offset; end date and end time of event; actions taken or treatments given; the severity of the event; event symptoms; diagnostic results; information about outcomes; and if the event is on-going what additional steps are planned.

4. Clinician Information Form (*completed once*):

This requires the clinician to record: the study clinician identification number, the clinician's name, the clinician's position at the clinic, the clinician's credentials (degree), and the clinician's contact information.

5. SBJ d/c Form (*completed as needed*):

This requires that a staff member specify that a subject has been withdrawn from, or quit, the protocol and the reason for why the subject is no longer participating.

ANALYSIS PLAN

The primary analysis for the study will be an evaluation of treatment response rates using an analysis of 2x2 contingency tables, using the Cochran-Mantel-Haenszel test to assess differences in treatment response by randomization groups, stratified by patient choice. The secondary analysis will evaluate how treatment non-responders and responders differ with respect to the various demographic and clinical profile measures.

CONFIDENTIALITY

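### The TES-versus-Sham secondary comparisons have no time point, analysis set or method, and the ISI has no post-baseline session common to stopped and continuing patients

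*Combined protocol and SAP*

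**What the plan says.** Secondary Outcomes states the aim: "Assess whether Nexalin TES produces significantly greater gains than Nexalin Sham for" depression (PHQ-9, QIDS), anxiety (GAD-7, POMS) and insomnia (ISI). It does not say when the gain is measured, in whom, or by what test.

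The Analysis Plan gives a Cochran-Mantel-Haenszel test for the response rate, stratified by ECT choice. It then says: "The secondary analysis will evaluate how treatment non-responders and responders differ with respect to the various demographic and clinical profile measures". That is a different question and not a randomised comparison. No analysis population or missing-data rule appears anywhere.

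Treatment length depends on early response. Under Procedures, patients who do not reach a 20% PHQ-9 reduction by the sixth treatment "will be designated treatment non-responders and discontinue their participation in the study while remaining as inpatients at the Carrier Clinic". Under Treatment, "Each patient will receive a minimum of 6 treatments and may receive up to 20 treatments", given twice a day, "Monday through Friday, over the course of 3-10 days". No later study assessment of those who stop is described.

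On timing, the Assessments paragraph says: "Assessments will be made at baseline (pre-treatment), twice daily, once daily, and once every 3 days (6 sessions"). QIDS, GAD-7 and POMS follow the 3-day schedule, and PHQ-9 is taken at each session. The ISI entry (Subject Measures, item 5) sets baseline and end of treatment: "This will be administered at the beginning and end of treatment (e.g., 1st and 10th session").

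**The concern.** Without a named time point, analysis set and method, each secondary comparison can be settled after the data are seen. For PHQ-9, QIDS, GAD-7 and POMS, wording alone can repair this, because the session-6 score will have been collected.

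For the ISI it cannot. The number of sessions before the last ISI depends on early PHQ-9 change, which treatment may affect. If TES improves early PHQ-9, more TES than Sham patients stay on, and their last ISI is taken later. Any general improvement over time, from inpatient care for example, then counts in favour of TES even if TES does nothing for insomnia. If the 10th-session example were applied literally, the ISI would be missing for everyone stopped at session 6. On either reading the session-6 ISI of continuers is never collected, and analysis cannot recover it.

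**Working it through.** **1. Schedule.** Two sessions a day over 3 to 10 days gives 2 × 3 = 6 to 2 × 10 = 20 sessions, which reproduces the plan's range. Every 6 sessions means sessions 6, 12 and 18.

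| Measure | Due at session 6, stopped patients | Due at session 6, continuers |
|---|---|---|
| PHQ-9 | yes | yes |
| QIDS, GAD-7, POMS | yes | yes |
| ISI | yes, as end of treatment | no; due at the last session, up to 20 |

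The schedule table marks the ISI as Pre-Post, a term used elsewhere for each session. The ISI entry itself says baseline and end of treatment, and I follow that. The enrolment figure of 150 has no stated inputs and cannot be reproduced; the point does not depend on it.

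**2. Last-score ISI comparison in all randomised patients.** All inputs are assumed, for illustration: baseline PHQ-9 mean 19, SD 4; early drop in Sham mean 4, SD 4.5; early TES effect 0.5 SD = 2.25 points; no TES effect on the ISI; correlation 0.5 between early PHQ-9 change and ISI change; every continuer gains a further g SD on the ISI after session 6.

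A patient stops if drop − 0.2 × baseline is below 0. This quantity has SD √(4.5² + (0.2 × 4)²) = 4.57.
- Sham: mean 4 − 3.8 = 0.2; exit = Φ(−0.2/4.57) = Φ(−0.044) = 0.483.
- TES: mean 6.25 − 3.8 = 2.45; exit = Φ(−2.45/4.57) = Φ(−0.536) = 0.296.

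False difference = g × (0.483 − 0.296) = 0.187g, in session-6 SDs.

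For the error rate, the variance of the last score in each arm is 1 + g²p(1 − p) + 2g × 0.5 × (4.5/4.57) × φ(k). Here p is the share continuing and k is 0.044 (Sham) or 0.536 (TES). At g = 1 the variances are 1.64 and 1.55, so the pooled SD is 1.26 and the standardised difference is 0.187/1.26 = 0.148. With 75 per arm, 0.148 × √(75/2) = 0.91, and the error is Φ(0.91 − 1.96) + Φ(−0.91 − 1.96) = 0.15.

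| Later gain g (SD) | False difference (session-6 SD) | Two-sided error, 75 v 75 |
|---|---|---|
| 0.25 | 0.05 | about 6% |
| 0.5 | 0.09 | about 8% |
| 1.0 | 0.19 | about 15% |

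Simulated trials with a t-test (20,000 per case) give 5.7%, 8.0% and 14.6%, and 5.0% with no later gain.

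**3. The same effect in ISI points.** Assume improvement of 0.1 to 0.3 points per session in both arms, and exits differing by 0.1 to 0.3. False difference = slope × difference in exits × (last session − 6). If continuers end at session 10: 0.1 × 0.1 × 4 = 0.04 to 0.3 × 0.3 × 4 = 0.36 points. If at session 20: 0.1 × 0.1 × 14 = 0.14 to 0.3 × 0.3 × 14 = 1.26 points.

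**4. What a session-6 comparison can detect.** With 75 per arm, two-sided 5% and no covariate adjustment, 0.5 SD gives 0.5 × √(75/2) = 3.06 and power Φ(3.06 − 1.96) = 86%. The QIDS asks about the last 7 days, and session 6 is treatment day 3. If the effect is diluted in proportion (an assumption), 0.5 × 3/7 = 0.21 SD and power is about 26%. If a weekend falls between treatment days, 0.5 × 5/7 = 0.36 SD and power is about 59%.

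**The case against.** **Every randomised patient may still have a post-baseline ISI.** This stands. A reader might infer that the ISI has no follow-up score at all, or that a last-score comparison is a selected one. The documents support neither. If end of treatment means each patient's own last session, stopped patients have an ISI at about session 6, and a comparison of all randomised patients by arm is unselected. It can also be read as the effect of assignment to TES with the stopping rule in place. What is missing is a common session, so equal exposure cannot be examined.

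**No continuers-only analysis is planned.** This also stands. A reader might infer that the secondary results will rest on patients who pass session 6. The plan does not say so; it is silent, and so does not exclude it.

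**The error scenario is strained.** In part. It needs an early PHQ-9 effect with no ISI effect and a substantial later gain in every continuer. This PHQ-9 was also modified to track nightly sleep through four items. If those enter the score, a PHQ-9 effect without an insomnia effect is less likely. They also record sleep through session 6, though not by the ISI. Inflation is small unless the later gain is large.

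**Session 6 is very early.** True. A questionnaire on a fixed later day for all patients is a legitimate alternative, and stopped patients remain inpatients. But their participation ends at exit and the usual ECT wait is given as 1 week, so later scores could include ECT and would estimate a different effect.

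**Conclusion.** The point holds for the secondary outcomes only. The time point, analysis set and method are absent on the face of the documents, and no assumption is needed to see it. The lack of a common post-baseline session is specific to the ISI and follows from the exit rule together with the ISI schedule.

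The size is illustrative: a false ISI difference of about 0.05 to 0.19 SD and a two-sided error of about 6% to 15%, under assumed exits of about 30% and 48% and a common later gain of 0.25 to 1.0 SD. With no later gain, or equal exits in the two arms, this false difference disappears. The reason to act now is that an uncollected session-6 ISI cannot be restored later.

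A reader might also infer that the primary response comparison is biased by the same mechanism. This point does not show that. How the 20% rule relates to the response definition is a separate matter to reconcile.

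**What to change.** 1. Subject Measures, item 5: replace the 10th-session example. Give the ISI at baseline, at session 6 to every patient before any exit, and at the last session of those who continue. Align the schedule table.
2. Analysis Plan: add a TES-versus-Sham comparison of PHQ-9, QIDS, GAD-7, POMS (naming the score) and ISI at session 6, in all randomised patients by assigned arm, adjusted for baseline score and ECT choice. If missing scores are imputed, the model should include treatment arm, baseline and the available PHQ-9 scores; omitting arm can pull the estimate towards zero.
3. Report end-of-treatment scores in all randomised patients as well, stating that exposure differs by early response. Do not present differences among continuers only as randomised effects.

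Cost: stopped patients already have an end-of-treatment ISI at session 6, so only continuers complete one more 2-minute form, at most 150 × 2 min = 5 hours in total. The stopping rule and sample size do not change. The downside is that session 6 misses later effects and the 7-day look-back dilutes the QIDS contrast, so the 86% power should not be quoted for it. The documents do not give the ISI look-back; if it is a week or more, the same caution applies.

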All participating staff and subjects will complete, in addition to the traditional paperwork and charting processes associated with standard clinical care, study documents via a password protected RedCap site on a Penn Server. These documents will be reviewed by the study coordinator on a daily basis and with the Penn PI on weekly basis. As needed reviews with the PI will occur given the incidence of an adverse event, the occurrence of treatment non-response, the incidence of patient non-adherence, or the occurrence of protocol deviations. In addition to the daily review of the study progress and problems, the study coordinator will speak on a bi-weekly basis with the Carrier Clinic coordinator and complete a checklist and notes form to document these encounters. The PI and coordinator will travel to the clinic once a month to discuss study logistics.

The study documents will include the following

- a) A subject identification form
- b) A study consent form (completed on paper w/ a signed digital copy sent to Penn staff via a secure upload method)
- c) 10 study questionnaires (e.g., the PHQ-9) completed by the patient via a RedCap site on a Penn Server according to a pre-determined schedule.
- d) 5 Tracking forms (re: patient contact, procedure details, and adverse events) completed by Carrier Clinic staff via a RedCap site on a Penn Server according to a pre-determined schedule

BACKGROUND

Electroconvulsive therapy (ECT), also referred to as “electroshock therapy,” is a psychiatric treatment where external electrical stimulation (brief-pulse currents of up to 800 millamps) is used to induce seizures. Treatments are administered, with anesthesia and muscle relaxants, 1-3 times per week over the course of several weeks, or until symptoms improve. ECT is very effective as an antidepressant, reducing depressive symptoms in approximately 50% of patients. Despite its effectiveness, it comes with significant risks. It can cause mild or severe confusion and memory loss, muscle soreness, worsening of symptoms in patients with neurologic disorders, and (as with any procedure that involves sedation), adverse effects from hypoxia. Finally, patients may also be disinclined to engage in this form of therapy owing to the social stigma associated with it and concerns about side effects. Accordingly, an alternative to ECT would be beneficial.

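### After session 6 no criterion covers lost response or worsening, and the section cited for stopping rules contains only tolerability stops

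*Combined protocol and SAP*

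**What the plan says.** The opening paragraph of Procedures contains the only response-based rule. Patients without a 20% fall in symptoms on the morning and afternoon PHQ-9 "on or before 6 treatments will be designated treatment non-responders and discontinue their participation in the study". The same paragraph notes that inpatient care is otherwise standard and that "they are receiving TES or Sham TES in place of ECT". It then refers the reader to the Protection Against Risks "section for stopping rules during treatment for subjects who do not show sufficient treatment response".

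The Treatment paragraph sets a minimum of 6 sessions and says a patient "may receive up to 20 treatments depending on whether an adequate treatment response is observed during the first 6 session". It makes no mention of response after that point.

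The assessment schedule has PHQ-9 at every session. A note in the Assessments paragraph reads: "All data acquired via this method (raw and summary data) will not be available to the Carrier Clinic collaborators during the study". The Confidentiality section agrees, giving back-end access to Penn staff only.

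The oversight text before Background has the Penn coordinator review study documents daily and the PI weekly. It adds: "As needed reviews with the PI will occur given the incidence of an adverse event, the occurrence of treatment non-response", among other triggers. The SBJ d/c form under Clinician Measures has staff "specify that a subject has been withdrawn from, or quit, the protocol" and give the reason, but sets no criterion for withdrawal.

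Protection Against Risks provides for stopping on persistent headache or nausea, poor electrode contact and agitation, and for the patient's off button. The rest covers rash, electrode removal, questionnaire distress and file storage.

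**The concern.** A reader who follows the cross-reference finds no rule about response. If the reference was meant for the 20% rule, that rule is applied once, by session 6. A patient who passes it can lose the gain, or rise above the baseline score, and still be eligible for treatment up to session 20.

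These are inpatients with major depression who have failed medication and been referred for ECT, and half of them receive no current. Usual care continues and clinicians can act on what they observe. However, the scores that would show a relapse earliest are closed to them, and the Penn staff who hold those scores are not told what to do with them.

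**Working it through.** **1. Reproduce the plan's session range.** Inputs from Procedures: 2 sessions per day, 3-10 days, Monday to Friday.
- Minimum: 2 × 3 = 6 sessions. Maximum: 2 × 10 = 20 sessions.
- Both match the Treatment paragraph, so the 10 days must be treatment days.

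**2. Sessions with no response criterion.**
- 20 − 6 = 14 sessions (sessions 7 to 20).
- 14 / 2 = 7 weekdays (treatment days 4 to 10).

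**3. Calendar span of treatment days 4 to 10**, assuming no missed sessions. With a Monday start they run from Thursday to the Friday of the following week, which is 9 days. Wednesday, Thursday and Friday starts also give 9. A Tuesday start runs from Friday to a Monday two weekends later, which is 11.

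**4. What applies in each phase.**

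| | Sessions 1-6 | Sessions 7-20 |
|---|---|---|
| Insufficient response | 20% PHQ-9 fall by session 6, otherwise discontinued | None |
| Worsening | No separate rule, but a steady worsener cannot show a 20% fall and is discontinued at session 6 | None |
| Tolerability stops | Yes | Yes |
| Treating clinic sees PHQ-9 | No | No |
| Penn review of documents | Daily and weekly, with the 20% rule to apply | Daily and weekly, with no threshold or action |

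**5. Trace one case (hypothetical).** Take a baseline PHQ-9 of 20. A 20% fall is 20 × 0.20 = 4 points, so a score of 16 at session 6 passes. If the score is back at 20 by session 10, the attenuation is (20 − 20) / 20 = 0%. No text in the protocol requires anyone to stop treatment or alert the physician, and 20 − 10 = 10 sessions remain available.

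**6. Which PHQ-9 decides session 6?** The rule allows the fall to occur on or before the sixth treatment. That can be read as any one reading up to then, as the session-6 reading, or as a morning and afternoon pair. The text does not choose.

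**7. Can a patient stopped later be classified for the primary outcome?** Yes. Primary Outcomes defines response as a 50% reduction or a score below 10, and a PHQ-9 exists for every session attended. The 20% continuation rule is a different test. A fall from 11 to 9 is 2 / 11 = 18%, which fails the 20% rule but is a response on the primary definition.

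**The case against.** The strongest reply is that the 20% rule in Procedures is itself the stopping rule for insufficient response, stated shortly before the cross-reference, so the defect is only a misdirected reference. That may be so, and the protocol nowhere expressly promises a rule for relapse. But on that reading the rule still ends at session 6.

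A second reply is that oversight covers the gap. Daily and as-needed review is not limited to the first six sessions, SAFTEE and QIDS are repeated every 3 days, and licensed staff see these inpatients twice each treatment day. Penn must already be able to tell the clinic to stop at session 6, so a line of communication is implied. All of this reduces the risk. It does not supply a threshold, an action or permission to share a score after session 6.

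Three stronger readings are tempting, and the documents do not support them.
- *No protection against worsening at any session.* Steady early worsening leads to discontinuation at session 6 under the 20% rule. Only a patient with some early improvement reaches the uncovered period.
- *Nine to eleven extra days without ECT.* Potential Study Risks gives a typical ECT wait of 1 week and a study delay of 3-5 days, which it places within normal waits. The span in the working counts treatment days with no response rule; it is not added delay. Patients who refuse ECT forgo no ECT they had accepted.
- *Later-stopped patients have no status in the primary response rate.* They can be classified from their PHQ-9. What is unstated is the assessment time, and that affects every patient.

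**Conclusion.** The concern holds in limited form. The cross-reference leads to a section with no response-based rule. No criterion for lost response or worsening applies in sessions 7 to 20, up to 14 sessions over 7 weekdays. Followed as written, the continuation rule and the data-access note together leave a relapsing patient on TES or sham with no trigger to stop or alert. The consequence is greatest for patients willing to have ECT, and undetected worsening matters for both groups.

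The session count rests on two sessions per weekday and a full course. How many patients would relapse after passing session 6, or pass it on a chance reading, cannot be sized because the documents give no PHQ-9 variability or relapse rate. The conclusion is textual and does not depend on such a figure. A reader might also infer that mandatory 20% stops are needed at later sessions. The protocol does not call for them, and they would remove some patients with partial improvement.

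**What to change.** 1. **Correct the cross-reference.** Put the session-6 rule in Protection Against Risks and state which PHQ-9 decides it.
2. **Add an alert after session 6.** If PHQ-9 is at or above baseline on two consecutive assessments, Penn staff notify the treating physician the same day. Write this as an explicit exception to the data-access note in Assessments. The physician decides whether to stop study treatment and return the patient to usual care, including ECT if accepted.
3. **Keep stopped patients in the Cochran-Mantel-Haenszel analysis.** Classify them by the Primary Outcomes definition at their last PHQ-9 on study treatment. Do not force them to non-response, since that could contradict the primary definition, as the 11-to-9 example shows for the 20% rule.

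No new assessment is needed, because PHQ-9 is already taken at each session. The cost is occasional same-day calls and a few discretionary stops. The alert conveys a score and does not reveal allocation.
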